9.6.1.5. Subgroup Analysis

Subgroup analyses for the primary efficacy endpoint based upon baseline demographic (age, gender, race, etc.) or baseline disease characteristics will be provided to determine the robustness of the treatment effect.

9.7. Safety Analysis

The safety analyses will be performed using the safety population, defined as all subjects who are randomized and receive at least one dose of investigational product.

Safety will be assessed by clinical review of all relevant parameters including treatment emergent adverse events (TEAEs), laboratory tests, vital signs, and ECG; no inferential testing for statistical significance will be performed. Data from safety assessments will be summarized descriptively for the Placebo-controlled Phase (Weeks 0 to 52) by the treatment group of CC-

90001 100 mg, 200 mg QD, 400 mg QD, and placebo; and for the CC-90001 Exposure Phase for subjects who receive at least one dose of CC-90001 treatment. For all safety analyses baseline will be relative to the first dose date following randomization at Week 0.

Adverse events will be classified using the MedDRA classification system. All TEAEs will be summarized by system organ class, preferred term, severity and relationship to investigational product. The TEAEs leading to death or to discontinuation from treatment and serious adverse events will be summarized and listed separately.

Data from other safety assessments will be summarized descriptively. Shift tables for laboratory parameters showing the number of subjects with values low, normal, and high comparing with the normal reference ranges pre-treatment versus post treatment will be provided.

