The binary efficacy endpoints will be summarized using counts and percentages. The treatment comparisons will be performed using the Cochran–Mantel–Haenszel (CMH) test adjusting for the stratification factors as appropriate. Missing values due to early termination will be imputed using data collected at the early termination visit if available; otherwise missing values will be imputed using the non-responder imputation (NRI) method.

The continuous efficacy endpoints will be summarized using mean, standard deviation (SD), median, minimum, maximum, and number of observations analyzed. The treatment comparisons will be performed using a mixed model of repeated measures (MMRM) as the primary analysis method and an analysis of covariance (ANCOVA) model as sensitivity analysis method for all continuous secondary efficacy endpoints.

The safety analyses for the 52-week placebo-controlled treatment phase will be performed using descriptive statistics based on the safety population, defined as all subjects who are randomized and receive at least one dose of IP. The safety analyses will also be performed for the CC-90001 exposure period for subjects who receive at least one dose of CC-90001, which will include safety data during the placebo-controlled treatment phase and active treatment phase.

An unblinded interim analysis will be performed after approximately 50% of subjects complete 52 weeks of treatment (as described in the DMC Charter).

TABLE OF CONTENTS

TITLE PAGE.....	1
PROTOCOL SUMMARY	6
1. INTRODUCTION.....	19
1.1. Disease Background	19
1.2. Compound Background.....	19
	
1.3. Rationale	27
1.3.1. Study Rationale and Purpose	27
1.3.2. Rationale for the Study Design	28
1.3.3. Rationale for Dose, Schedule and Regimen Selection	28
	
2. STUDY OBJECTIVES AND ENDPOINTS.....	30
3. OVERALL STUDY DESIGN	35
3.1. Study Design	35
3.2. Study Duration for Subjects.....	38
3.2.1. Early Termination Visit	38
3.2.2. Lost to Follow-up	38
3.3. End of Trial	38
4. STUDY POPULATION	40
4.1. Number of Subjects	40
4.2. Inclusion Criteria	40
4.3. Exclusion Criteria	42
5. TABLE OF EVENTS.....	46
6. PROCEDURES	53
6.1. Screening Phase.....	53
6.2. Treatment Period	55
6.2.1. Unscheduled Visits	57
6.3. Early Termination.....	57
6.4. Post-treatment Observational Follow-up Phase	58

6.5. Safety Assessments..... 58
6.5.1. Physical Examination 58
6.5.2. Electrocardiogram 59
6.5.3. Clinical Laboratory Assessments 59
6.5.4. Action Plan for Monitoring Potential Hepatotoxicity 60

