Subjects who sign informed consent form (ICF) prior to the implementation of Protocol Amendment 4 will have an option to participate in a double-blind active treatment phase. After 52 weeks of placebo-controlled treatment all placebo subjects will be re-randomized 1:1 by IWRS to the 200 mg QD or 400 mg QD dose groups at Week 54. Prior to the implementation of Protocol Amendment 4, subjects were also re-randomized into a 100 mg QD dose group. The subjects who were previously re-randomized to the 100 mg dose group will remain in the 100 mg dose group. Subjects who were initially randomized to active treatment arms will remain in their assigned dose groups through the end of the active treatment phase.

Subjects who sign ICF after the implementation of Protocol Amendment 4 will receive treatment in a double-blind placebo-controlled treatment phase only.

Subjects will have regularly scheduled visits to assess efficacy, safety, tolerability, [REDACTED] PK [REDACTED]; refer to [Table 3](#), Table of Events.

All subjects who discontinue prematurely from the study at any time will be required to enter the 4-week Post-treatment Observational Follow-up Phase.

The study will be conducted in compliance with the International Council for Harmonisation (ICH) of Technical Requirements for Registration of Pharmaceuticals for Human Use/Good Clinical Practice (GCP) and applicable regulatory requirements.

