6.2. Treatment Period

The subject will begin treatment upon confirmation of eligibility. For all subsequent visits, an administrative window of ± 3 days is permitted except Visit 15/Week 53 and Visit 16/Week 54 (for the subjects who participate in the active treatment phase). Visit 15/Week 53 should be performed 7 to 10 days after Visit 14/Week 52 and Visit 16/Week 54 (for the subjects who participate in the active treatment phase) should be performed 7 to 10 days after Visit 15/Week 53. Scheduling of Visits 3 to 14 is based on Visit 2/Week 0 (randomization date) and scheduling of Visits 17 to 27 (for the subjects who participate in the active treatment phase) is based on Visit 16/Week 54 (re-randomization date). 

Visit 5 Week 8 and Visit 7 Week 16 will be remote visits. Assessments performed at these visits have been specified in the Table of Events, [Table 3](#)

The following evaluations will be performed at the frequency specified in the Table of Events, [Table 3](#). The evaluations should be performed prior to dosing on the visit day, unless otherwise specified.

- Adverse event evaluation (continuously)
- Concomitant medications evaluation (continuously)
- Concomitant procedures evaluation (continuously)
- Counseling about pregnancy precautions and the potential risks of fetal exposure
- Complete physical examination (Section 6.5.1)
- Targeted physical examination (Section 6.5.1)
- Vital signs and weight (Section 6.1)

- 12-lead ECG (Section 6.5.2)
- Clinical Laboratory Evaluations (Section 6.5.3):
 - Hematology panel
 - Coagulation tests
 - Chemistry panel
 - Urinalysis and urine cytology
 - Serum pregnancy test
 - Urine pregnancy test at Visit 5 Week 8 and Visit 7 Week 16
 - Urine EtG test
 - Fecal occult blood test (FOBT)
- Efficacy assessment (Section 6.6):
 - Liver biopsy/histology

- Investigational product (IP) dispensation: The Principal Investigator, Sub-investigator, or Study Coordinator should make an effort to witness subjects taking their first dose and record the date and time in the source document record. Subjects are instructed to take 3 tablets of IP QD, approximately the same time of day (preferably in the morning), with or without food. Visit 5/Week 8 and Visit 7/Week 16 will be remote visits and IP will be dispensed at Visit 4/Week 4 and Visit 6/Week 12 for these 2 visits.
- Investigational product (IP) return (all used and unused blister cards) and IP compliance assessment (Section 7.6)

6.2.1. **Unscheduled Visits**

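### The Week 0 baseline in Section 9.7 gives placebo subjects who start CC-90001 at Week 54 a reference value at least 375 days before their first dose of drug

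*Combined protocol and SAP*

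**What the plan says.** Section 9.7 describes two sets of safety summaries. One covers the Placebo-controlled Phase by treatment group. The other is "for the CC-90001 Exposure Phase for subjects who receive at least one dose of CC-90001 treatment". The next sentence fixes the reference point: "For all safety analyses baseline will be relative to the first dose date following randomization at Week 0". The section also plans laboratory shift tables "comparing with the normal reference ranges pre-treatment versus post treatment will be provided", without saying which treatment start is meant.

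The statistical methods part of the Protocol Summary describes the exposure-period analysis as one "which will include safety data during the placebo-controlled treatment phase and active treatment phase".

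Under Section 3.1, subjects who consented before Amendment 4 "will have an option to participate in a double-blind active treatment phase". After the placebo-controlled year, "all placebo subjects will be re-randomized 1:1 by IWRS to the 200 mg QD or 400 mg QD dose groups at Week 54"; before the amendment, 100 mg was also a re-randomization option. Subjects first randomized to CC-90001 stay on their dose. Section 9.1 defers analysis details to a separate SAP, which is not in the text reviewed.

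**The concern.** The Exposure Phase set holds two kinds of subject. Those randomized to CC-90001 at Week 0 have a first study dose that is also their first CC-90001 dose, so a Week 0 baseline suits them. Placebo subjects re-randomized at Week 54 (*switchers* below) have a first study dose of placebo. The rule in Section 9.7 gives them a pre-placebo value, and no other section resets it.

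Any change-from-baseline or pre-versus-post entry built on that value combines a year on placebo with the time on drug. It can hide a change that occurred on CC-90001 or suggest one that did not. Take hypothetical ALT values with an assumed upper limit of normal of 40:

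- **Hidden change.** ALT is 60 at Week 0, 30 just before CC-90001 and 60 on CC-90001. Against Week 0 the change is 60 − 60 = 0, high to high. Against the pre-drug value it is 60 − 30 = +30, normal to high.
- **Apparent change.** ALT is 30 at Week 0, 60 just before CC-90001 and 60 on CC-90001. Against Week 0 the change is +30, normal to high. Against the pre-drug value it is 0.

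The purpose of the Exposure Phase summary is to describe safety on CC-90001, and for switchers this reference does not do that.

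**Working it through.** **Inputs**

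- Visits 3 to 14 are scheduled from Week 0, and the Week 52 visit has a window of ±3 days (Section 6.2).
- "Visit 15/Week 53 should be performed 7 to 10 days after Visit 14/Week 52" (Section 6.2).
- The Week 54 visit "should be performed 7 to 10 days after Visit 15/Week 53" (Section 6.2). Switchers start CC-90001 at that visit.
- Visits 17 to 27 are scheduled from Week 54, and Week 102 has a window of ±3 days (Section 6.2, Table 3).
- Screening may begin up to 10 weeks before Week 0 (Table 3).

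**The plan's own figure.** Nominal Week 54 is 54 × 7 = 378 days. Building it from the visits gives 52 × 7 + 7 + 7 = 378 days, which agrees.

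**Gap from Week 0 to a switcher's first CC-90001 dose**

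- Week 52 visit: 364 ± 3 = day 361 to day 367.
- Shortest: 361 + 7 + 7 = 375 days (53.6 weeks).
- Longest: 367 + 10 + 10 = 387 days (55.3 weeks).

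**Tests without a Week 0 value.** Table 3 schedules ECG, urine cytology and the fecal occult blood test (FOBT) at Screening but not at Week 0. Their gap can reach 387 + 70 = 457 days. Liver tests may also reach back before Week 0 in some subjects: Section 6.1 and Appendix C (footnote b) build the baseline from at least two measurements four or more weeks apart when specified screening values are raised.

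**Share of the interval before any CC-90001, at Week 102.** Week 54 to Week 102 is 48 × 7 = 336 ± 3 days, or 333 to 339.

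- Smallest: 375 / (375 + 339) = 52.5%.
- Largest: 387 / (387 + 333) = 53.8%.

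**Gap if the last value before the first CC-90001 dose were used.** The visits are those marked in Table 3. Fasting is required at Week 52 but not listed for Week 53 (Section 6.5.3).

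| Parameter | Last scheduled pre-drug value | Gap to first CC-90001 dose |
|---|---|---|
| Vital signs, weight | Week 54, before dosing | 0 days |
| Hematology; chemistry other than glucose and lipids | Week 53 | 7–10 days |
| ECG, PT/INR, urinalysis, urine cytology; fasting glucose and lipids | Week 52 | 7 + 7 = 14 to 10 + 10 = 20 days |
| FOBT | Week 48 (day 333 to 339) | 375 − 339 = 36 to 387 − 333 = 54 days |

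**The case against.** The case against runs as follows.

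- **No affected table is named.** Section 9.7 lists no change-from-baseline table for the Exposure Phase, and its shift tables use a pre-treatment value rather than baseline. If pre-treatment means before CC-90001, the shift-table part of the problem disappears. This stands as a limit on the claim, but the baseline sentence still covers every safety analysis and the shift tables still lack a defined reference.
- **The Protocol Summary may already exclude the placebo year.** It speaks of an exposure period, which for a switcher would naturally start at the first CC-90001 dose. That is a fair reading. It concerns which data are counted and leaves the baseline rule unchanged.
- **The SAP may settle it.** It may, but a phase-specific baseline there would contradict the word *all* in Section 9.7.
- **Few subjects are affected.** About 10 to 15 subjects were expected in the 100 mg arm by Amendment 4. *Assuming* equal allocation until then, placebo would hold a similar number before opt-outs and dropouts. Against 60 + 60 + 10 to 15 subjects randomized to CC-90001, that is 10/140 = 7% to 15/150 = 10% of the exposed set. The documents do not state the earlier ratio, and subjects who consented before the amendment but were randomized after it could add to the number. The figure is illustrative only, but a small group is plausible.
- **The replacement baseline has weaknesses.** For liver tests, switchers would have one Week 53 value where some other subjects have a two-measurement baseline. The sponsor itself notes, in the Amendment 4 justification, that ALT and AST fluctuate. Week 53 is also the biopsy visit, and the order of blood draw and biopsy is not stated. In the first ALT example, the fix reports normal to high for a subject who only returned to the pre-study value. These points stand as costs. They do not make a value more than a year old the better reference for change on drug.
- **Time is not bias.** The 52.5% to 53.8% is a share of calendar time and does not measure bias in any safety parameter. This is correct.

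**Conclusion.** The concern holds. Section 9.7 states a rule, and for switchers in the Exposure Phase that rule gives the wrong reference. The size is a gap of 375 to 387 days for parameters measured at Week 0, and up to 457 days for those last scheduled at Screening. These figures assume visits within their windows and a baseline value taken on or before the Week 0 first dose.

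The consequence is confined to change-from-baseline or pre-versus-post entries for switchers that use this baseline. The randomized Weeks 0 to 52 comparison and subjects first randomized to CC-90001 are unaffected. Safety summaries carry no inferential testing, and the DMC reviews unblinded safety data separately (Section 9.9.3). The effect on any reported safety result cannot be calculated because the number of switchers is not given. It should be corrected, mainly because the correction is cheap.

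**What to change.** 1. In Section 9.7, limit the Week 0 baseline sentence to the Placebo-controlled Phase.
2. For the Exposure Phase, keep the existing baseline for subjects randomized to CC-90001, including any two-measurement liver-test baseline under Section 6.1.
3. For placebo subjects re-randomized to CC-90001, define the Exposure Phase baseline as the last non-missing value before the first CC-90001 dose, with one exception: glucose and lipids use the last fasting value.
4. Define pre-treatment in the Exposure Phase shift tables by the same rule.
5. State that switchers contribute on-treatment data to this phase only from their first CC-90001 dose, and align the sentence in the Protocol Summary.

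The change concerns summary tables only and leaves the baseline used for Appendix C monitoring as it is.

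The cost is a short edit to Section 9.7 and the Protocol Summary, plus one extra derived baseline in the SAP and programming. No new assessments are needed. The second baseline is a post-randomization value and, for liver tests, a single measurement; a table footnote should say so.

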9.8. Interim Analysis

An unblinded futility analysis will be performed after approximately 50% of subjects complete 52 weeks of treatment. The DMC will review the totality of the available data to determine the following options:

- Continue the study as planned
- Terminate the study for futility
- Stop enrolling a treatment arm due to futility if not fully enrolled at interim analysis

The details of the interim analysis will be documented in the DMC Charter.

Additional interim analyses may be conducted.

9.9. Other Topics

9.9.2. Internal Safety Management Team

In addition to ongoing safety monitoring conducted by Investigators and individual study personnel, cumulative and interval blinded AEs, SAEs, discontinuations due to AEs, and abnormal laboratory findings will be reviewed internally by the Celgene Safety Management Team (SMT). The review will follow the Council for International Organizations for Medical Sciences, Working Group VI (CIOMS VI) recommendations. The SMT is comprised of lead representatives from multiple Celgene functions engaged in the CC-90001 development

program. The scope, conduct, processes, and accountabilities are specified by Celgene Standard Operating Procedure (SOP).

9.9.3. External Data Monitoring Committee

Safety monitoring will also be performed by an external, independent DMC. A DMC will be convened that will include physician experts with experience in treating subjects with NASH and a statistician, all of whom are not otherwise involved in the study conduct and for whom there is no identified conflict of interest. During the course of the study, the DMC will review the unblinded safety data regularly as well as safety and efficacy data in accordance with the guidelines for the preplanned interim analyses. An independent third party will prepare the reports of aggregate data summaries and individual subject data listings, as appropriate, to the DMC members for each scheduled meeting. Operational details for the DMC will be detailed in the DMC Charter.

10. ADVERSE EVENTS

10.1. Monitoring, Recording and Reporting of Adverse Events

An AE is any noxious, unintended, or untoward medical occurrence that may appear or worsen in a subject during the course of a study. It may be a new intercurrent illness, a worsening concomitant illness, an injury, or any concomitant impairment of the subject's health, including laboratory test values (as specified by the criteria in Section 10.3), regardless of etiology. Any worsening (ie, any clinically significant adverse change in the frequency or intensity of a pre-existing condition) should be considered an AE. A diagnosis or syndrome should be recorded on the AE page of the CRF rather than the individual signs or symptoms of the diagnosis or syndrome.

Abuse, withdrawal, sensitivity or toxicity to an investigational product should be reported as an AE. Overdose, accidental or intentional, whether or not it is associated with an AE should be reported on the overdose CRF. (See Section 7.2 for the definition of overdose.) Any sequela of an accidental or intentional overdose of an investigational product should be reported as an AE on the AE CRF. If the sequela of an overdose is an SAE, then the sequela must be reported on the AE CRF. The overdose resulting in the SAE should be identified as the cause of the event on the AE CRF but should not be reported as an SAE itself.

In the event of overdose, the subject should be monitored as appropriate and should receive supportive measures as necessary. There is no known specific antidote for CC-90001 overdose. Actual treatment should depend on the severity of the clinical situation and the judgment and experience of the treating physician.

All subjects will be monitored for AEs, including AEs related to SARS-CoV-2 infection, during the study. Assessments may include monitoring of any or all of the following parameters: the subject's clinical symptoms, laboratory, pathological, radiological or surgical findings, physical examination findings, or findings from other tests and/or procedures.

All AEs will be recorded by the Investigator from the time the subject signs informed consent until 28 days after the last dose of IP as well as those SAEs made known to the Investigator at any time thereafter that are suspected of being related to IP. Adverse events and SAEs will be recorded on the AE page of the CRF and in the subject's source documents. All SAEs that occur after first dose of IP must be reported to Celgene Drug Safety within 24 hours of the Investigator's knowledge of the event via Electronic Data Capture (EDC) system.

10.2. Evaluation of Adverse Events

A qualified Investigator will evaluate all adverse events as to:

10.2.1. Seriousness

An SAE is any AE occurring at any dose that:

- Results in death;
- Is life-threatening (ie, in the opinion of the Investigator, the subject is at immediate risk of death from the AE);

- Requires inpatient hospitalization or prolongation of existing hospitalization (hospitalization is defined as an inpatient admission, regardless of length of stay);
- Results in persistent or significant disability/incapacity (a substantial disruption of the subject's ability to conduct normal life functions);
- Is a congenital anomaly/birth defect;
- Constitutes an important medical event.

Important medical events are defined as those occurrences that may not be immediately life-threatening or result in death, hospitalization, or disability, but may jeopardize the subject or require medical or surgical intervention to prevent one of the other outcomes listed above. Medical and scientific judgment should be exercised in deciding whether such an AE should be considered serious.

Events **not considered** to be SAEs are hospitalizations for:

- a standard procedure for protocol therapy administration. However, hospitalization or prolonged hospitalization for a complication of therapy administration will be reported as an SAE.
- routine treatment or monitoring of the studied indication not associated with any deterioration in condition.
- the administration of blood or platelet transfusion as routine treatment of studied indication. However, hospitalization or prolonged hospitalization for a complication of such transfusion remains a reportable SAE.
- a procedure for protocol/disease-related investigations (eg, surgery, scans, endoscopy, sampling for laboratory tests, bone marrow sampling). However, hospitalization or prolonged hospitalization for a complication of such procedures remains a reportable SAE.
- hospitalization or prolongation of hospitalization for technical, practical, or social reasons, in absence of an AE.
- a procedure that is planned (ie, planned prior to start of treatment on study); must be documented in the source document and the CRF. Hospitalization or prolonged hospitalization for a complication remains a reportable SAE.
- an elective treatment of or an elective procedure for a pre-existing condition, unrelated to the studied indication, that has not worsened from baseline.
- emergency outpatient treatment or observation that does not result in admission, unless fulfilling other seriousness criteria above.

If an AE is considered serious, the AE screen of the eCRF must be completed and ticked 'serious'.

For each SAE, the Investigator will provide information on severity, start and stop dates, relationship to the IP, action taken regarding the IP, and outcome.

